17.0 Confidentiality

A. Confidentiality of Study Data

Describe the local procedures for maintenance of confidentiality of study data and any records that will be reviewed for data collection.

17.1 A. Where and how will all data and records be stored? Include information about: password protection, encryption, physical controls, authorization of access, and separation of identifiers and data, as applicable. Include physical (e.g. paper) **and** electronic files.

Response: Data collected from participants will be coded with a participant number. Subject identifiers (e.g., name, address, birth date) will be kept separate from other data in a locking cabinet in the PI's South Campus office ([name]). Thus the signed consent forms and master list of participants will be in a secure location accessible to the PI and co-researchers. Data will be retained for a minimum of three years. Digital data such as video tape will be kept on a password protected server. If manuscripts related to this work continue to be generated at the end of three years the data will be maintained until all manuscripts have been published.

17.2 A. How long will the data be stored?

Response:

Data will be stored a minimum of three years

17.3 A. Who will have access to the data?

Response:

Research personnel

17.4 A. Who is responsible for receipt or transmission of the data?

Response:

Research personnel

17.5 A. How will the data be transported?

Response:

Data will be coded and entered into computerized spreadsheets accessible on a secure drive.

B. Confidentiality of Study Specimens

Describe the local procedures for maintenance of confidentiality of study specimens.

N/A: No specimens will be collected or analyzed in this research.
(*Skip to Section 19.0*)

17.6 B. Where and how will all specimens be stored? Include information about: physical controls, authorization of access, and labeling of specimens, as applicable.

Response:

17.7 B. How long will the specimens be stored?

Response:

17.8 B. Who will have access to the specimens?

Response:

17.9 B. Who is responsible for receipt or transmission of the specimens?

Response:

17.10 B. How will the specimens be transported?

Response:

18.0 Provisions to Monitor the Data to Ensure the Safety of Subjects

N/A: This study is not enrolling subjects, or is limited to records review procedures only. This section does not apply.

NOTE: Minimal risk studies may be required to monitor subject safety if the research procedures include procedures that present unique risks to subjects that require monitoring. Some examples include: exercising to exertion, or instruments that elicit suicidality or substance abuse behavior. In such cases, N/A is not an acceptable response.

18.1 Describe the plan to periodically evaluate the data collected regarding both harms and benefits to determine whether subjects remain safe.

Response:

Data will be reviewed by the PI on a quarterly basis. If concerns or comments from participants arise they will be noted and discussed by

research members. We want to ensure the participant's well-being in the study and promote a positive experience without compromising the integrity of the research. Serious events and problems will be reported by the primary investigator to the SBSIRB in a within 24 hours.

18.2 Describe what data are reviewed, including safety data, untoward events, and efficacy data.

Response:

Performance on assessments of movement, and strength will be reviewed. In addition, performance on the Upper Limb Training will be reviewed.

18.3 Describe any safety endpoints.

Response:

Participants will safely complete the technology guided upper limb Training.

18.4 Describe how the safety information will be collected (e.g., with case report forms, at study visits, by telephone calls with participants).

Response: Participants will be monitored during data collection in aim 1. In aim 2, participants will start the technology guided upper limb Training in the lab with direct mentoring and then progress to completing it independently at home. At the start of the in-home program, members from the research team will either go to the participant's home to confirm that the system is working correctly or will use a platform such as skype to converse with the participant and see the set up. Research members will work with participants if they experience technical difficulties by going to their house, skype or a phone conversation. They will be provided with contact information for the PI and other research personnel in case they have concerns or difficulties at home. Participants will also be asked about their in home upper limb training experience at their post-intervention testing.

18.5 Describe the frequency of safety data collection.

Response:

Quarterly or within 24 hours of a participant raising a concern.

18.6 Describe who will review the safety data.

Response:

The PI

18.7 Describe the frequency or periodicity of review of cumulative safety data.

Response:

Quarterly

18.8 Describe the statistical tests for analyzing the safety data to determine whether harm is occurring.

Response:

Participants will be debriefed following training, if they report concerns about the in-home training these will be recorded and evaluated by the research personnel. If participants call in to report concerns, these will be recorded and considered by research personnel.

18.9 Describe any conditions that trigger an immediate suspension of the research.

Response: If participants report concerns that the research team deems could cause difficulties for all participants, research will be suspended.

19.0 Withdrawal of Subjects

N/A: This study is not enrolling subjects. This section does not apply.

19.1 Describe anticipated circumstances under which subjects may be withdrawn from the research without their consent.

Response: If participants fail to complete the testing sessions in Aim 1 in a timely manner, they may be withdrawn from the study.

Participants will be assessed with the Berg Balance Scale. If they do not score above a 42, they will only perform exercises in a seated position in Aim2. If participants report pain with activities in the program and the program cannot be modified to eliminate pain, the participant will be taken out of the study.

19.2 Describe any procedures for orderly termination.

NOTE: Examples may include return of study drug, exit interview with clinician. Include whether additional follow up is recommended for safety reasons for physical or emotional health.

Response: Exit interview with research personnel. If balance concerns have prompted termination in the training portion of the study, the PI will consult with the participant. The participant will need to return the rehabilitation device and fill out the paper work for payment of the pre-intervention testing session.

19.3 Describe procedures that will be followed when subjects withdraw from the research, including retention of already collected data, and partial withdrawal from procedures with continued data collection, as applicable.

Response:

Data collected prior to participant's departure from the study may be used in portions of the data analyses.

20.0 Risks to Subjects

20.1 List the reasonably foreseeable risks, discomforts, hazards, or inconveniences to the subjects related to their participation in the research. Consider physical, psychological, social, legal, and economic risks. Include a description of the probability, magnitude, duration, and reversibility of the risks.

NOTE: Breach of confidentiality is always a risk for identifiable subject data.

Response Risks to the Subjects

It is possible for the participant to experience:

- fatigue
- loss of balance, possibly resulting in a fall
- a muscle strain or orthopedic injury
- breach of confidentiality with your personnel information

20.2 Describe procedures performed to lessen the probability or magnitude of risks, including procedures being performed to monitor subjects for safety.

Risks to participants are minimized by:

- screening participants using the inclusion/exclusion criteria
- providing the participants with rests as they wish between assessments
- tailoring the Upper Limb Training program to the abilities of each participant
- reminding participants that they can terminate their participation at any time, without penalty.
- Coding data used in analyses

20.3 If applicable, indicate which procedures may have risks to the subjects that are currently unforeseeable.

Response:

The Upper Limb Training is a new approach to rehabilitation at home. It is possible that participants may have difficulties with this home exercise program. To reduce risks, participants who score at or below 42 on the Berg Balance Scale must complete all home exercises in a seated position. The Training program will also be tailored to each participant's abilities.

20.4 If applicable, indicate which research procedures may have risks to an embryo or fetus should the subject be or become pregnant.

Response:

The procedures should not cause increased risk to the embryo or fetus.

20.5 If applicable, describe risks to others who are not subjects.

Response:

The procedures should not cause risk to others who are not subjects.

21.0 Potential Benefits to Subjects

21.1 Describe the potential benefits that individual subjects may experience by taking part in the research. Include the probability, magnitude, and duration of the potential benefits. Indicate if there is no direct benefit.

NOTE: Compensation cannot be stated as a benefit.

Response: It is unlikely that participants in Aim 1 will experience a direct physical benefit for their participation in the study. It is possible that participants that complete aim 2 may experience some level of benefit in their ability to move their arm/hand. The results of the study may influence rehabilitation approaches in the future. All participants may derive satisfaction from the potential to help others. The risk to benefit ratio is excellent.

22.0 Compensation for Research-Related Injury

N/A: The research procedures for this study do not present risk of research related injury (e.g. survey studies, records review studies). This section does not apply.

22.1 If the research procedures carry a risk of research related injury, describe the available compensation to subjects in the event that such injury should occur.

Response:

Safety precautions will be taken to limit the risks to participants in the study to “minimal risk”. The Upper Limb Training may involve activities in standing, making it possible that the participant may fall. By assessing individuals for fall risk, using a clinical assessment, prior to enrollment into aim 2 of the study, we will lower the risk to the participant.

If a participant feels like they have been injured because of taking part in this study. They should inform the PI and they will be encourage to consult with their physician. Treatment options will be explained by your physician. Generally, this care will be billed to you, your insurance or other third party. The University at Buffalo has no program to pay for medical care for research-related injury.

22.2 Provide a copy of contract language, if any, relevant to compensation for research related injury.

*NOTE: If the contract is not yet approved at the time of this submission, submit the current version here. If the contract is later approved with **different language regarding research related injury**, you must modify your response here and submit an amendment to the IRB for review and approval.*

Response:

NA

23.0 Economic Burden to Subjects

23.1 Describe any costs that subjects may be responsible for because of participation in the research.

NOTE: Some examples include transportation or parking.

Response: No costs are associated with participation in the research

- N/A:** This study is not enrolling subjects, or is limited to records review procedures only. This section does not apply.

24.0 Compensation for Participation

25.1 Describe the amount and timing of any compensation to subjects, including monetary, course credit, or gift card compensation.

Response:

If you agree to take part in the first part of this research study, we will pay you \$30 for your time and effort. The paperwork for the check will be completed at the testing session. Processing payment may take 4-6 weeks.

If you have had a stroke and agree to take part in the second part of this research study, we will pay you \$25 each for the pre and post intervention testing sessions and \$200 for completing the 11 week in home Upper Limb Training program (5 weeks baseline and 6 weeks training). This will be a total of \$300. The paperwork for the check will be completed at the last testing session. If participants do not complete the training program, they will be asked to bring the equipment back to Kimball Tower and will complete the paperwork for payment of the pre-test sessions. Processing payment may take 4-6 weeks.

- N/A:** This study is not enrolling subjects, or is limited to records review procedures only. This section does not apply.
- N/A:** There is no compensation for participation. This section does not apply.

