10.0 Study Timelines

10.1 Describe the anticipated duration needed to enroll all study subjects.

Response:

It is anticipated that all participants will be enrolled within two years of the start of the study.

10.2 Describe the duration of an individual subject's participation in the study. Include length of study visits, and overall study follow-up time.

Response:

Aim 1: Participants will come to Kimball Tower on South Campus three times for approximately 1 hour each session.

Aim 2: Participants with stroke will be asked to come to Kimball Tower a total of 4 times (2 pre-tests and 2 post-tests) and participate in a 10 week in-home technology guided exercise program. Pre and post testing will be done in the two weeks pre and post the exercise program. The caregiver feedback measures would obtain information from caregivers in one session lasting 5-30 minutes depending on the amount of feedback the caregiver provides. We could conduct the interview over the phone on or near the last day of the testing session or the caregiver can do it in person during the participant's 3rd or 4th testing sessions.

10.3 Describe the estimated duration for the investigators to complete this study (i.e. all data is collected and all analyses have been completed).

Response:

It is anticipated that data collection and analyses will be completed in 2-2.5 years.

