Aim 1: In a study (N=15 young adults) we will examine the ability of the smartphone to accurately identify the above listed components for the ADLs listed in Table 1. Each participant will be asked to perform five repetitions of each activity in three different testing sessions. We will qualify the performance of our activity recognition algorithms using accuracy and area under the receiver-operator characteristic (ROC) curve (AUC). We will perform an evaluation with random hold out and cross-validation as well as leave-one-person-out evaluation. Particularly, we will compute sensitivity, specificity, and F-measure values. Then we will generate a learning curve that plots classification accuracy as a function of training set size and will add data collection time until the curve plateaus. Our previous research work has shown that it is critical to collect enough sensor training data in building robust models. Similarly, we will consider recruiting new participants until the curve plateaus.

Aim 2: Sample size estimation was based on the repeated measures ANOVA test of within subjects change in standardized assessment scores from baseline to follow-up. With $\alpha = 0.05$, power = 0.8, 4 measurements, and a desired effect size (f) = 0.25 to detect, a sample size of 15 participants is needed. This effect size is consistent with studies on functional activity performance and recovery following stroke.⁶⁸ A total of 20 participants will be recruiting to account for a 25% attrition rate.

16.3 Describe any procedures that will be used for quality control of collected data.

Validation of the system in aim 1 acts as a quality control.

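### The plan provides no post-test for participants who stop training early, so the Wolf Motor and 9-hole peg change would in effect be estimated in completers

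*Combined protocol and SAP*

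**What the plan says.** Section 24.0 covers people who do not finish the home program: "If participants do not complete the training program, they will be asked to bring the equipment back to Kimball Tower". There they "will complete the paperwork for payment of the pre-test sessions". Section 19.2 lists "Exit interview with research personnel", a consultation with the investigator if balance concerns led to termination, and then: "The participant will need to return the rehabilitation device and fill out the paper work for payment of the pre-intervention testing session". None of these steps is an outcome test.

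The template question at 19.3 asks about partial withdrawal with continued data collection. The whole response is: "Data collected prior to participant's departure from the study may be used in portions of the data analyses".

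Section 19.1 says that where activities cause pain and "the program cannot be modified to eliminate pain, the participant will be taken out of the study".

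Section 16.1 plans a repeated measures ANOVA of the Wolf Motor and 9-hole peg tests at four times, the two ends of baseline and the two ends of follow-up. ΔT is the score at the start of follow-up minus the score at the end of baseline. Section 16.2 bases the Aim 2 sample size on this ANOVA: 15 are needed, and 20 are recruited to "account for a 25% attrition rate". No analysis population, missing-data method or sensitivity analysis is given.

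**The concern.** Recruiting 20 to keep 15 protects the number of complete records. It does not protect against selection. If the people who stop are those for whom training hurts or does not suit, the ones left to be post-tested are a favourable subset. Pain is a named reason for removal, and Section 19.2 foresees termination over balance concerns, so losses unrelated to outcome cannot be taken for granted.

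At stake is what ΔT means. The stated goal is a home system for people with lasting deficits after stroke. An average over finishers answers how much finishers improve. It does not answer how much people who start on the system improve. Once the device is back and the person has gone, the missing scores can be replaced only by assumptions that the data cannot test.

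**Working it through.** **1. The plan's own figure.** Inputs from Section 16.2: 15 needed, 25% attrition. 15 / (1 − 0.25) = 20, which matches. The plan therefore allows for 20 − 15 = 5 people without a full set of assessments. (The 15 depends on a correlation between assessments that is not stated. With noncentrality f²·n·m/(1 − ρ), f = 0.25, m = 4 and sphericity, it is reached at ρ of about 0.69 to 0.70. This does not affect the present point.)

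**2. Which records yield ΔT.** ΔT needs the end-of-baseline and start-of-follow-up scores. A person who stops during training has the first but is given no occasion for the second. A person lost after the first post-test has a ΔT, but lacks the fourth value that a standard repeated measures ANOVA requires. A person lost during baseline never started training. The 25% is not split among these groups, so 5 stoppers is an upper bound.

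**3. Illustration of size.** Assume 15 completers with mean gain g (improvement, whichever way the score runs) and k stoppers with mean gain r·g. The all-starters mean is g(15 + rk)/(15 + k). The completers' figure therefore overstates it by (15 + k)/(15 + rk) − 1. The values of r are assumptions; the documents give none. The row k = 2 shows a case below the upper bound.

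| Stoppers k | r = 1 (equal gain) | r = 0.5 | r = 0 | r = −0.5 (worsen) |
|---|---|---|---|---|
| 5 | 20/20: 0% | 20/17.5: 14% | 20/15: 33% | 20/12.5: 60% |
| 2 | 17/17: 0% | 17/16: 6% | 17/15: 13% | 17/14: 21% |

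In SD units with an assumed g = 0.5 and k = 5, the all-starters mean is 0.5 at r = 1, 0.75 × 0.5 + 0.25 × 0.25 = 0.4375 at r = 0.5, and 0.75 × 0.5 = 0.375 at r = 0.

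**4. Effect on power.** Assume a paired two-sided test at 0.05 and a within-group SD of change of 1. Fifteen completers then have 80% power at a standardized change of 0.78. If 5 stoppers are also tested, power with 20 is about 0.91 if they gain equally, 0.81 if they gain half as much, and 0.65 if they gain nothing. Testing stoppers does not always raise power; in the last case it falls because the average effect is smaller.

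**5. Is one extra test enough?** No. A score at equipment return still leaves the end-of-follow-up value missing, so an ANOVA restricted to complete records would drop the person anyway. The analysis has to change too.

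**The case against.** The strongest reply is that ΔT is not the main test. Section 16.1 accepts the Aim 2 hypothesis on a significant positive trend during training, from visual inspection and ARIMA models of each person's own smartphone data. Someone who stops early still has baseline probes and some training data, which 19.3 allows to be used. This stands and limits the point. ΔT nevertheless has a stated role in validating the training effect, and the ANOVA containing it sets the sample size.

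Second, no sentence forbids a post-test, and the lead quotation comes from a payment paragraph. A reader might infer that the plan bars testing after stopping. The documents do not support that; they only fail to provide for it. The payment, termination and withdrawal texts agree in that silence.

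Third, a reader might take 25% as the rate of stopping training, or 33% as the expected bias. Neither is supported. The 25% is overall attrition, and every bias figure above, including zero, rests on an assumed gain.

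Fourth, the effect among people who complete training is a legitimate target for a small single-group study whose aim is to examine performance changes. That also stands. But the plan does not say it has chosen that target, and without stoppers' scores nobody can tell whether the two targets differ.

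**Conclusion.** The concern holds for the Wolf Motor and 9-hole peg analysis. As written, ΔT would in effect be a completers' estimate, because the plan neither tests those who stop nor says how their missing scores are handled. The size of the bias is unknown. With 15 completers and the upper bound of 5 stoppers, it runs from 0% (equal gain) through 14% (half the gain) to 33% (no gain), and beyond if stoppers worsen; fewer stoppers shrink it. A reader might infer that the whole of Aim 2 is a completers' result. The documents do not support that, because the main decision rests on within-participant trends that can use partial data. What remains is a real gap in the validating analysis, and it should be closed before participants begin to stop.

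**What to change.** **Sections 19.2, 19.3 and 24.0.** Separate stopping training from leaving the study. Leave every rule on when training stops, including the pain rules, unchanged; only measurement is affected, and only by invitation. Invite anyone who began training and stops, if willing, to do the Wolf Motor and 9-hole peg tests at the equipment-return visit or at the scheduled start-of-follow-up visit. Record the test date and pay the usual $25. State whether the invitation extends to people taken out of the study for pain, so that 19.1 and the new text agree.

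**Section 16.1.** Replace the repeated measures ANOVA, which in its usual form needs complete records, with a mixed model for repeated measures that uses all available assessments from everyone who started training. Report completers as a secondary analysis. Scores taken at an early return will not fall exactly at the start of follow-up, so show a sensitivity analysis that excludes them.

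**Cost.** Section 24.0 pays $25 per testing session (4 × $25 + $200 = the stated $300), so the added payment is at most about 5 × $25 = $125, plus some staff time and consent wording. Some people will decline or not return. For them the mixed model still relies on an assumption about the missing scores, so the number should be reported with reasons.
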